APPENDIX 5.

Rivermead Mobility Index
Example form

Value of the **Rivermead Mobility Index** corresponds to the score assigned to a question to which the doctor can give a positive answer regarding the patient. The index value can range from 0 (inability to perform any voluntary movements independently) to 15 (ability to run 10 metres).

No.	Skill	Question
1	Turns in bed	Can you turn from your back to your side without assistance?
2	Transition from the supine position to the sitting position.	Can you sit on the edge of the bed by yourself from the supine position?
3	Maintaining balance in a sitting position.	Can you sit on the edge of your bed without support for 10 seconds?
4	Transition from sitting to standing.	Can you stand up (from any chair) in less than 15 seconds and hold a standing position beside the chair for 15 seconds (using your arms or, if required, aids)?
5	Standing without support	The patient is observed to stand unsupported for 10 seconds.
6	Relocation	Can you move from bed to chair and back again without any assistance?
7	Walking around the room, including with aids if necessary.	Can you walk 10 metres using aids if necessary, but without the assistance of a stranger?
8	Climbing the stairs	Can you climb one flight of stairs without assistance?
9	Walking outside the flat (on a flat surface)	Can you walk outside your flat, on the pavement without assistance?
10	Walking around the room without the use of aids.	Can you walk 10 metres within the flat without a crutch, orthosis and without the assistance of another person?
11	Lifting objects off the floor	If you drop something on the floor, can you walk 5 metres, pick up the object you dropped and walk back?
12	Walking outside the flat (on uneven ground)	Can you walk outside your flat on uneven ground (grass, gravel, snow, etc.) without assistance?
13	Taking a bath	Can you get in and out of the bathtub (shower cubicle) without supervision and wash yourself?
14	Climbing and descending 4 steps	Can you climb up 4 steps and back down without leaning on the handrail, but using aids if necessary?
15	Running	Can you run 10 metres without limping in 4 seconds (fast walking is allowed)?

APPENDIX 6.

Hospital Anxiety and Depression Scale (HADS)
Example form

Part I (assessing the level of ANXIETY)

I'm feeling tense, I'm uncomfortable

3 - all the time

2 - often

1 - occasionally, sometimes

1 - never

I feel scared, like something terrible is about to happen

3 - definitely it is, and the fear is very great

2 - yes, that's true, but the fear is not very great

1 - sometimes, but it doesn't bother me

1 - never

Anxious thoughts are running through my head

3 - permanently

2 - most of the time

1 - once in a while and not too often

It is easy for me to sit back and relax

0 - definitely, it is

1 - I guess that's true

2 - only occasionally, that's true

3 - I cannot do it at all

I feel an inner tension or trembling

4 - never

1 - sometimes

2 - often

3 - very often

I'm restless, I constantly need to move around

4 - definitely, it is

2 - I guess that is true

1 - only to some extent, that is true

0 - not at all

I get a sudden sense of panic

3 - very often

2 - quite often

1 - not so often

0 - not at all

Part II (assessment of the level of DEPRESSION)

Something that gave me great pleasure still gives me the same feeling now

0 - definitely, it is

1 - I guess that is true

2 - only in a very small way, that's true

3 - it's not like that at all

I am capable of laughing and seeing the funny in an event

4 - definitely, it is

- 1 - I guess that is true
- 2 - only in a very small way, that's true
- 3 - completely incapable

I feel invigorated

- 4 - never
- 2 - very rarely
- 1 - sometimes
- 2 - practically all the time

I feel like I've been taking things very slowly

- 3 - practically all the time
- 2 - often
- 1 - sometimes
- 1 - not at all

I don't look after my appearance

- 3 - definitely, it is
- 2 - I don't spend as much time on it as I should
- 1 - maybe I've been spending less time on it
- 0 - I look after myself the same way I used to

I find that what I do (activities, hobbies) can bring me a sense of fulfilment

- 0 - just like always
- 1 - yes, but not as much as I used to
- 2 - much less than usual
- 3 - I don't think so at all

I can enjoy a good book, radio - or TV programme

- 0 - often
- 1 - sometimes
- 2 - rarely
- 3 - very rarely

Number of points:

0-7 points - Normal

8-10 points - subclinical symptoms

More than 11 points - clinically significant symptoms

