Trial Schedule:	
The trial includes the following stages:
 
 - Screening - preliminary examination of patients. - Randomization and initiation of therapy - randomization, initiation of trial therapy. - Therapy period - use of investigational product/placebo + standard therapy, patient assessment, registration of AE.
Trial duration:	The total duration of patient participation in the trial will be no more than 74 days, including the screening period.
Efficacy criteria:	
Primary efficacy criterion:
 
 - The magnitude of change in the patient's mRS (Modified Rankin Scale) score at the end of therapy vs. baseline (in points). 
Secondary efficacy criteria:
 
 - The magnitude of change in the patient's mRS (Modified Rankin Scale) score at the end of parenteral therapy vs. baseline (in points). - Proportion of disabled patients (mRS score 3 or more) at the end of therapy; - Proportion of disabled patients (mRS score 3 or more) at the end of parenteral therapy; - Proportion of patients with mRS score 0-1 at the end of therapy; - Proportion of patients with mRS score 0-1 at the end of parenteral therapy; - The magnitude of change in the patient's NIHSS (National Institutes of Health Stroke Scale) score at the end of therapy vs. baseline (in points). - The magnitude of change in the patient's NIHSS (National Institutes of Health Stroke Scale) score at the end of parenteral therapy vs. baseline (in points). - The magnitude of change in the patient's MoCA cognitive status score at the end of therapy vs. baseline (in points). - The magnitude of change in the patient's MoCA cognitive status score at the end of parenteral therapy vs. baseline (in points). - The magnitude of change in the patient's Rivermead Mobility Index score at the end of therapy vs. baseline (in points). - The magnitude of change in the results of the patient's state assessment by the Rivermead mobility index at the end of the parenteral course of therapy vs. baseline (in points). - The magnitude of change in the patient's HADS score at the end of therapy vs. baseline (in points). - The magnitude of change in the patient's HADS score at the end of parenteral therapy vs. baseline (in points).

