6.3.11. Patient assessment using specialised scales

Conducted according to the trial procedure schedule to assess the patient's condition for subsequent analyses of therapy efficacy using the following scales:

- mRS (Modified Rankin Scale) - score on Visits 0, 2, 4;
- NIHSS (The National Institutes of Health Stroke Scale) - score on Visits 0, 2, 4;
- Montreal Cognitive Assessment Scale MoCA - score on Visits 1, 2, 4;
- Hospital Anxiety and Depression Scale (HADS) - scores on Visits 1, 2, 4;
- Rivermead Mobility Index - score on Visits 1, 2, 4.

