7.1. Efficacy parameters under trial

According to the purpose and objectives of the present trial, the efficacy of the investigational product vs. comparator product will be assessed by the following parameters:

Primary efficacy criterion:

- The magnitude of change in the patient's **mRS** (Modified Rankin Scale) score at the end of therapy vs. baseline (in points).

Secondary efficacy criteria:

- The magnitude of change in the patient's **mRS** (Modified Rankin Scale) score at the end of parenteral therapy vs. baseline (in points).
- Proportion of disabled patients (**mRS** score 3 or more) at the end of therapy;
- Proportion of disabled patients (**mRS** score 3 or more) at the end of parenteral therapy;
- Proportion of patients with mRS score 0-1 at the end of therapy;
- Proportion of patients with mRS score 0-1 at the end of parenteral therapy;
- The magnitude of change in the patient's **NIHSS** (National Institutes of Health Stroke Scale) score at the end of therapy vs. baseline (in points).
- The magnitude of change in the patient's **NIHSS** (National Institutes of Health Stroke Scale) score at the end of parenteral therapy vs. baseline (in points).
- The magnitude of change in the patient's **MoCA** cognitive status score at the end of therapy vs. baseline (in points).
- The magnitude of change in the patient's **MoCA** cognitive status score at the end of parenteral therapy vs. baseline (in points).
- The magnitude of change in the patient's **Rivermead** Mobility Index score at the end of therapy vs. baseline (in points).
- The magnitude of change in the results of the patient's state assessment by the **Rivermead** mobility index at the end of the parenteral course of therapy vs. baseline (in points).
- The magnitude of change in the patient's **HADS** score at the end of therapy vs. baseline (in points).
- The magnitude of change in the patient's **HADS** score at the end of parenteral therapy vs. baseline (in points).

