APPENDIX 4.

Montreal Cognitive Assessment Scale (MoCA) *Example form*

Guidelines for application and evaluation

The Montreal Cognitive Assessment Scale (MoCA) was developed as a rapid assessment tool for moderate cognitive dysfunction. It assesses various cognitive domains: attention and concentration, executive functions, memory, language, visual-constructional skills, abstract thinking, numeracy and orientation. The time to perform a MoCA is approximately 10 minutes. The maximum possible score is 30 points; 26 points or more is considered normal.

1. Creating an Alternating Pathway:

Application: The investigator instructs the subject, "Please draw a line going from number to letter in ascending order. Start here [point to (1)] and draw a line from 1, then to A, then to 2, and so on. Finish here [dot (D)]."

Evaluation: One point is awarded if the testee successfully draws a line as follows: 1-A-2-B-3-C-3-D-4-E-5-F, without crossing lines. Any error that is not immediately corrected by the testee him(her)self earns 0 points.

2. Visual Constructive Skills (Cube):

Application: The Investigator gives the following instructions while pointing to the cube: "Copy this drawing as accurately as you can in the space below the drawing."

Evaluation: One point is awarded when the drawing is accurately executed:

- The drawing should be three-dimensional;
- All the lines are drawn;
- There are no extra lines;
- The lines are relatively parallel and their lengths are the same (rectangular prism is acceptable).

No point is given if any of the above criteria are not met.

3. Visual Constructive Skills (Hours):

Application: Point to the right third of the available space on the form and give the following instructions: "Draw a clock. Spread out all the numbers and give the time as 10 minutes past 12."

Evaluation: One point is assigned for each of the following three items:

- Contour (1 point): The dial must be circular, only a slight curvature (i.e. a slight imperfection in the closing of the circle) is allowed;
- Numerals (1 point): all numerals on the watch must be represented, with no additional numbers; numerals must stand in the correct order and be placed in the appropriate quadrants on the dial; Roman numerals are acceptable; numerals: may be placed outside the outline of the dial;

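### As printed, the HADS key in Appendix 6 is inconsistent on 8 of 14 items and would mis-score two secondary endpoints if it is the key in use

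*Protocol*

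**What the plan says.** Protocol 7.1 lists two HADS secondary criteria: "The magnitude of change in the patient's HADS score at the end of parenteral therapy vs. baseline (in points" and "The magnitude of change in the patient's HADS score at the end of therapy vs. baseline (in points". Section 6.3.11 sets the assessments: "Hospital Anxiety and Depression Scale (HADS) - scores on Visits 1, 2, 4". SAP sections 1 and 6 carry the same two endpoints, and SAP Table 6 is a generic summary template for the scale.

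Item scoring appears only in Protocol Appendix 6, headed as an example form. It prints a digit beside each response to 14 items, seven for anxiety (among them "I feel an inner tension or trembling") and seven for depression, and then three bands: 0-7 normal, 8-10 subclinical, and more than 11 clinically significant. A score of 11 falls in no band. Neither document says whether the HADS endpoint is the total or the two subscales.

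**The concern.** The endpoints are differences in summed digits, so they depend on each item falling by one point for each step of improvement. On eight items the printed digits do not do that. The worst cases are "I feel an inner tension or trembling" and "I am capable of laughing and seeing the funny in an event", where the least symptomatic answer carries the highest digit on the item. Most of the faults sit at the mild end of the items, which is where a patient who recovers finishes. If the digits were applied as printed, real improvement in mood or anxiety would be under-recorded there, or recorded as worsening on some items, in both HADS endpoints.

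**Working it through.** **Inputs.** All digits come from Protocol Appendix 6, put in order from the most to the least symptomatic answer. The reference is internal: six items on the same form (relax, panic, pleasure, appearance, fulfilment, book) run 3, 2, 1, 0.

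| Item | Printed, worst to best | Fault |
|---|---|---|
| "I'm feeling tense, I'm uncomfortable" | 3, 2, 1, 1 | no 0; last step tied |
| "I feel scared, like something terrible is about to happen" | 3, 2, 1, 1 | no 0; last step tied |
| Anxious thoughts | 3, 2, 1 | zero option missing |
| Inner tension | 3, 2, 1, 4 | best answer scores highest |
| Restless | 4, 2, 1, 0 | 3 skipped |
| Laughing | 3, 2, 1, 4 | best answer scores highest |
| Invigorated | 4, 2, 1, 2 | best answer scores above *sometimes* |
| Slowed down | 3, 2, 1, 1 | no 0; last step tied |

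**Count.** Five of 7 anxiety items and 3 of 7 depression items, so 8 of 14. Seven have wrong or duplicated digits and one lacks an option.

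**Score levels as printed**, in form order, with anxious thoughts at its lowest printed option:

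- Best answer throughout: anxiety 1+1+1+0+4+0+0 = 7; depression 0+4+2+1+0+0+0 = 7; total 14 (13 if anxious thoughts is left blank). A 0-3 key gives 0.
- Mildest-symptom answer throughout: 1 on each item, total 14. A 0-3 key also gives 14.
- Worst answer throughout: anxiety 3+3+3+3+3+4+3 = 22; depression 3+3+4+3+3+3+3 = 22; total 44. A 0-3 key gives 42.

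**Change from mildest to best on every item.**

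- Seven items fall by 1 (the six intact items and restless): −7.
- Inner tension and laughing each rise by 3: +6.
- Invigorated rises by 1: +1.
- Tense, scared, slowed down and anxious thoughts do not move: 0.
- Net: −7 + 6 + 1 = 0. With every item scored 0-3 the change is −14, or −13 if anxious thoughts keeps only its three options.

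**Largest possible improvement (worst to best).** Printed: 44 − 14 = 30. With a 0-3 key: 42 − 0 = 42. By item, the 30 is 6×3 = 18 from the intact items, 3×2 = 6 from the tied items, 2 from anxious thoughts, 4 from restless, 2 from invigorated, and −1 each from inner tension and laughing.

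**What survives in a change score.** An excess that is equal at both visits cancels. Here the excess over a 0-3 key is 14 at the best answers, 14 − 14 = 0 at the mildest-symptom answers and 44 − 42 = 2 at the worst, so it varies with the response and does not fully cancel.

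**The case against.** The strongest reply is that these digits are not a scoring rule at all. Each printed 4 opens an item directly after an item whose last line is numbered 3, which looks like a list counter running on. Each duplicated 1 stands on a last line where a 0 would be expected, and the missing option looks like a dropped line. Similar damage occurs elsewhere: in section 6.6 the last bullet is fused with the heading of section 7. The form is only an example, the sites are in Russia, Kazakhstan and Uzbekistan, and sections 4.8, 13.2 and 13.3 allow electronic capture of scale results and use eCRFs. Nothing makes this English page the operative key.

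Much of this stands. An artefact is plausible and the text alone cannot settle it; the run-on is not universal, since the book item follows an item ending in 3 yet starts at 0. Equally, neither document contains another HADS key, and section 11.8 requires investigators to follow the approved protocol. The reply therefore supports checking the source page and the eCRF rather than leaving the appendix as it is.

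A reader might infer three stronger things that the documents do not support:

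- *The endpoints are already corrupted.* Nothing shows that the printed digits were used.
- *The arm difference is biased toward zero or reversed.* Reversal is shown only for the last step of three items. Worst to best on the whole form still moves in the right direction (44 to 14), and the 4-to-2 step on restless and invigorated enlarges improvement. Direction and size depend on response patterns that are not given.
- *A symptom-free score of 14 is the harm.* It is a level, and no endpoint uses the bands. Each subscale's 7 is still in the printed normal band; only if the bands apply to the total, which the form does not say, would 14 leave it.

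**Conclusion.** The point holds conditionally. As printed, the only HADS key in the documents is inconsistent on 8 of 14 items. If it is the key in use, both HADS change endpoints are mis-scored: the last step of improvement raises the score on three items and earns nothing on three others, mildest to best on every item nets 0 points instead of about 14, and the largest possible improvement is 30 instead of 42.

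This rests on two assumptions: that the source page really prints these digits, and that sites or the eCRF score with them. Any between-arm bias is of unknown size and direction. Two of the 13 secondary criteria in Protocol 7.1 are concerned; the mRS primary endpoint and the sample size are not.

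**What to change.** 1. Check Appendix 6 against the source page and correct it so that every item has four options scored 0-3 in the same order as the six intact items, including the missing option for anxious thoughts. In the same pass, assign the score of 11 to a band.
2. Confirm that the operative site form and the eCRF scoring key match the corrected form.
3. Only if the printed digits were used, rescore from the ticked response text, not the digit, before database lock. A response to anxious thoughts taken on a three-option form cannot be recovered this way and should be noted as a limitation.

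The cost is a form correction, a key check and possibly some rescoring.

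As a separate minor item, correct the MoCA trail key in Appendix 4. It reads "1-A-2-B-3-C-3-D-4-E-5-F", which uses 3 twice and ends at F although the instruction finishes at D. It affects at most 1 of 30 points and has no bearing on the HADS point.

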CTCAE - Common Toxicity Criteria for Adverse Events;
GCP - Good Clinical Practice;
HADS - Hospital Anxiety and Depression Scale;
ITT - Intent-to-treat population, includes all randomized patients regardless of investigational product/placebo administration
MedDRA - Medical Dictionary for Regulatory Activities;
mITT - modified Intent-to-treat population includes patients who have completed the full course of therapy, regardless of the presence of violations/ deviations from the Protocol;
MoCA - Montreal Cognitive Assessment Scale;
mRS - Modified Rankin Scale;
NIHSS - National Institutes of Health Stroke Scale;
PP - Per protocol population includes patients who completed the trial according to the Protocol.
In the tables of efficacy and safety of the medicinal products Mexidol® solution for intravenous and intramuscular injection, 50 mg/ml (RPC PHARMASOFT LLC, Russia) and Mexidol® FORTE 250 film-coated tablets, 250 mg (RPC PHARMASOFT LLC, Russia) vs. placebo the following parameters of descriptive statistics will be given:
N - number of valid observations;
Mean - arithmetic mean;
Median - middle point in a dataset
Min - minimum value;
Max - maximum value;
Q₁ - lower quartile;
Q₃ - upper quartile;

Version 1.0 of 12.11.2021

Protocol-Specific Version for Protocol #PHS-APIS-004-MEX-SOL-TAV. version 1.3 dated 07.06.2021

CONFIDENTIAL

page 8 of 58

Plan for statistical analysis of efficacy and safety parameters

SD - standard deviation;

CV - coefficient of variation.

1. Trial background

Trial title: Prospective international multicentre randomized, double-blind, placebo-controlled, parallel-group clinical trial to evaluate the safety and efficacy of Mexidol® solution for intravenous and intramuscular administration, 50 mg/ml (RPC Pharmasoft LLC, Russia) and Mexidol® FORTE 250 film-coated tablets, 250 mg (RPC PHARMASOFT LLC, Russia) in their sequential use in patients in the acute and early recovery periods of ischaemic stroke (MIR).

Protocol No.: PHS-APIS-004-MEX-SOL-TAB, version 1.3 dated 07.06.2021

Sponsor: RPC PHARMASOFT LLC, Russia

Investigational product: Mexidol® solution for intravenous and intramuscular injection, 50 mg/ml (RPC PHARMASOFT LLC, Russia) 10 ml (500 mg) BID by intravenous drip in 100-200 ml of 0.9% NaCl solution for 10 days and Mexidol® FORTE 250 film-coated tablets, 250 mg (RPC PHARMASOFT LLC, Russia) 1 tablet TID for the next 60 days.

Comparison product: Placebo 1, solution for intravenous and intramuscular injection, 10 ml BID by intravenous drip in 100-200 ml of 0.9% NaCl solution for 10 days and Placebo 2, film-coated tablets, 1 tablet TID for the next 60 days.

Development Phase: III

Trial design: A prospective multicentre, randomized, double-blind, parallel-group comparative clinical trial.

Number of patients: 304

Purpose of the trial: comparative evaluation of efficacy and safety of therapy with Mexidol® solution for intravenous and intramuscular administration, 50 mg/ml (RPC PHARMASOFT LLC, Russia) and Mexidol® FORTE 250 film-coated tablets, 250 mg (RPC PHARMASOFT LLC, Russia) in comparison with placebo during their sequential use in patients in the acute and early recovery periods of ischaemic stroke.

Trial objectives:

1. To evaluate the efficacy of Mexidol® solution for intravenous and intramuscular injection, 50 mg/ml (RPC PHARMASOFT LLC, Russia) and Mexidol® FORTE 250 film-coated tablets, 250 mg (RPC PHARMASOFT LLC, Russia) during their sequential use in patients in the acute and early recovery periods of ischaemic stroke vs. placebo.

2. To carry out a comparative evaluation of the frequency and severity of adverse events of Mexidol® solution for intravenous and intramuscular injection, 50 mg/ml (RPC PHARMASOFT LLC, Russia) and Mexidol® FORTE 250 film-coated tablets, 250 mg (RPC PHARMASOFT LLC, Russia) during their sequential use in patients in the acute and early recovery periods of ischaemic stroke vs. placebo.

Additional objective: To carry out a comparative evaluation of pharmacodynamic effects of Mexidol® solution for intravenous and intramuscular administration, 50 mg/ml (RPC PHARMASOFT LLC, Russia) and Mexidol® FORTE 250 film-coated tablets, 250 mg (RPC PHARMASOFT LLC, Russia) during their sequential use in patients in the acute and early recovery periods of ischaemic stroke vs. placebo.

Version 1.0 of 12.11.2021

Protocol-Specific Version for Protocol #PHS-APIS-004-MEX-SOL-TAV. version 1.3 dated 07.06.2021

CONFIDENTIAL

page 9 of 58

Plan for statistical analysis of efficacy and safety parameters

Primary endpoint:

The magnitude of change in the patient's mRS (Modified Rankin Scale) score at the end of therapy vs. baseline (in scores).

Secondary endpoints:

1. The magnitude of change in the patient's mRS (Modified Rankin Scale) score at the end of parenteral therapy vs. baseline (in scores).
2. Proportion of disabled patients (mRS score 3 or more) at the end of therapy vs. baseline;
3. Proportion of disabled patients (mRS score 3 or more) at the end of parenteral therapy vs. baseline;
4. The magnitude of change in the patient's NIHSS (National Institutes of Health Stroke Scale) score at the end of therapy vs. baseline (in scores).
5. The magnitude of change in the patient's NIHSS (National Institutes of Health Stroke Scale) score at the end of parenteral therapy vs. baseline (in scores).
6. The magnitude of change in the patient's MoCA cognitive status score at the end of therapy vs. baseline (in scores).
7. The magnitude of change in the patient's MoCA cognitive status score at the end of parenteral therapy vs. baseline (in scores).
8. The magnitude of change in the patient's Rivermead Mobility Index score at the end of therapy vs. baseline (in scores).
9. The magnitude of change in the results of the patient's state assessment by the Rivermead mobility index at the end of the parenteral course of therapy vs. baseline (in scores).
10. The magnitude of change in the patient's HADS score at the end of therapy vs. baseline (in scores).
11. The magnitude of change in the patient's HADS score at the end of parenteral therapy vs. baseline (in scores).

Criteria for assessing pharmacodynamic effects:

1. The magnitude of change in the results of assessment of LPO activity (malonic dialdehyde) and AOS indicators (superoxide dismutase, Se-dependent glutathione peroxidase) at the end of therapy vs. baseline;
2. The magnitude of change in the results of assessment of LPO activity (malonic dialdehyde) and AOS indicators (superoxide dismutase, Se-dependent glutathione peroxidase) at the end of the parenteral course of therapy vs. baseline;
3. The magnitude of change in the results of evaluation of laboratory parameters reflecting ED (Willebrandt factor, endothelin 1, homocysteine) and antihypoxant effect (hypoxia-inducible factor HIF-1 α , lactate, neuron-specific enolase) at the end of therapy vs. baseline;
4. The magnitude of change in the results of evaluation of laboratory parameters reflecting ED (Willebrandt factor, endothelin 1, homocysteine) and antihypoxant effect (hypoxia-inducible factor HIF-1 α , lactate, neuron-specific enolase) at the end of the parenteral course of therapy vs. baseline.

Version 1.0 of 12.11.2021

Protocol-Specific Version for Protocol #PHS-
APIS-004-MEX-SOL-TAV. version 1.3 dated
07.06.2021

CONFIDENTIAL

page 10 of 58

Plan for statistical analysis of efficacy and safety parameters

Safety parameters

Safety and tolerability will be assessed throughout the trial (from first use of the investigational product/placebo) using the following data:

1. AE/SAE reports data,
2. Physical examination data, vital signs (BP, HR, respiratory rate, body temperature),
3. Indicators of laboratory analyses and instrumental methods of examination.

A conclusion on the safety of the investigational product will be made after statistical evaluation of all AEs, including serious SAEs with at least a possible association with the use of the investigational product.

Applicable significance level: probability of a 1st kind of error is set at 5%. As an interim analysis of the primary endpoint data is planned, a genus I error correction approach α ($\alpha = 0.0294$) will be used to prove the hypothesis of "superiority" of investigational product therapy vs. placebo therapy for the primary efficacy criterion.

2. Purpose of data statistical analysis

The purpose of the development of this Statistical Analysis Plan is to describe the planned analysis of efficacy and safety data in the "Prospective international multicentre randomized double-blind placebo-controlled parallel-group clinical trial to evaluate the efficacy and safety of Mexidol® solution for intravenous and intramuscular administration, 50 mg/ml (RPC PHARMASOFT LLC, Russia) and Mexidol® FORTE 250 film-coated tablets, 250 mg (RPC PHARMASOFT LLC, Russia) in their sequential use in patients in the acute and early recovery periods of ischaemic stroke (IS)" under protocol #PHS-APIS-004-MEX-SOL-TAB, version 1.3 dated 07.06.2021, for inclusion of the results in the Clinical Trial Report.

The results obtained according to the planned statistical analysis of the data presented in this document will be used in the submission of the registration dossier for the drug to the regulatory authorities, as well as in the writing of publications on the materials of the conducted clinical trial.

The trial will be conducted in accordance with the Protocol, in strict compliance with applicable regulatory requirements, including but not limited to:

- Constitution of the Russian Federation;
- Current version of the Federal Law of the Russian Federation dated 21 November 2011 No. 323-FZ "On the Fundamentals of Health Protection of Citizens in the Russian Federation";
- Current version of the Federal Law of the Russian Federation No. 61-FZ "On Circulation of Medicines" dated 12 April 2010;
- Current version of the Federal Law of the Russian Federation dated 27 July 2006 N 152-FZ "On Personal Data"
- Order of the Ministry of Health of the Russian Federation No. 200 n of 01.04.2016. "On Approval of the Rules of Good Clinical Practice";
- Russian National Standard GOST R 52379-2005 "Good Clinical Practice", which complies with the standards of the International Conference on Harmonisation of Technical Requirements for Registration of Pharmaceutical Products for Human Use (ICH) Good Clinical Practice Guidelines (ICH-GCP);

Version 1.0 of 12.11.2021

Protocol-Specific Version for Protocol #PHS-APIS-004-MEX-SOL-TAV. version 1.3 dated 07.06.2021

CONFIDENTIAL

page 11 of 58

Plan for statistical analysis of efficacy and safety parameters

- Rules of Good Clinical Practice of the Eurasian Economic Union, approved by the Decision of the Council of the Eurasian Economic Commission dated 3 November 2016 No. 79;
- Rules of Compulsory Life and Health Insurance for Patients Participating in Clinical studies of a Medicinal Product approved by Resolution of the Government of the Russian Federation No. 714 dated 13 September 2010;
- Resolution of the Government of the Russian Federation No. 393 dated 18 May 2011 "On Amendments to the Model Rules for Compulsory Life and Health Insurance for Patients Participating in Clinical studies of a Medicinal Product";
- Rules of the International Conference on Harmonisation of Technical Requirements for Registration of Medicinal Products for Human Use;
- The World Medical Association's 1964 Declaration of Helsinki, most recently revised (Fortaleza, 2013);
- Guidelines for Expertise of Medicinal Products of FGBU NCESMP of the Ministry of Health of Russia (Moscow, 2013)
- Order of the Federal Service for Healthcare Oversight No. 1071 dated 15.02.2017 "On Approval of the Procedure for Pharmacovigilance";
- Order of the Ministry of Health and Social Development of the Russian Federation No. 757n dated 26.08.2010 "On Approval of the Procedure for Monitoring the Safety of Medicinal Products for Medical Use, Registration of Adverse Actions, Serious Adverse Reactions, Unexpected Adverse Reactions in the Use of Medicinal Products for Medical Use";

Statistical evaluation of efficacy and safety parameters will be performed in accordance with the Drug Evaluation Guidelines (Volume I. - FGBU NCESMP, Moscow, 2014), Guidelines on the principles of application of biostatistics in clinical trials of medicinal products (Annex to the recommendation of the EEC Collegium from 03.11.2020 No. 2014) and general recommendations on biomedical statistics (ICH Topic E9 Statistical Principles for Clinical Trials, CPMP/ICH/363/96, 1998; Sergienko V.I., Bondareva I.B. Mathematical Statistics in Clinical Trials, Moscow: GEOSTAR-Media, 2006).

3. Deviations from protocol

A statistical plan has been prepared and will be agreed prior to the statistical analysis. Statistical analyses were planned according to the Clinical Trial Protocol. Deviations from the protocol in statistical analyses are not planned. Any deviation from the protocol is permitted only in an emergency or after written authorization from the Sponsor. If there is a deviation from the planned statistical analysis, all changes will be identified compared to the methods described in the statistical analysis plan. Similarly, if any additional changes are required after the analysis has been performed, this will be reflected in the Clinical Trial Report. All deviations of the present from the statistical analysis plan with their justification will be reported in the Clinical Trial Report. No changes will be made to the list of parameters to be evaluated. Statistical analysis methods may be changed if this would facilitate a more correct and informative analysis, any changes will be described and justified in the final Clinical Trial Report.

Version 1.0 of 12.11.2021

[figure not shown]
Protocol-Specific Version for Protocol #PHS-APIS-004-MEX-SOL-TAV. version 1.3 dated 07.06.2021

CONFIDENTIAL

page 12 of 58

Plan for statistical analysis of efficacy and safety parameters

4. Trial procedures

5. Randomization

Table 1. Randomization scheme developed by Smooth Drug Development

Country	Block number	Randomization code	Therapy
Republic of Kazakhstan	001	616	B
Republic of Kazakhstan	001	174	A
Republic of Kazakhstan	001	637	B
Republic of Kazakhstan	001	869	A
Republic of Kazakhstan	2	455	A
Republic of Kazakhstan	2	548	B
Republic of Kazakhstan	2	687	A
Republic of Kazakhstan	2	809	B
Republic of Kazakhstan	3	810	B
Republic of Kazakhstan	3	680	A
Republic of Kazakhstan	3	294	A
Republic of Kazakhstan	3	513	B
Republic of Kazakhstan	4	180	A
Republic of Kazakhstan	4	467	B
Republic of Kazakhstan	4	986	A
Republic of Kazakhstan	4	365	B
Republic of Kazakhstan	5	865	A
Republic of Kazakhstan	5	678	B
Republic of Kazakhstan	5	671	B
Republic of Kazakhstan	5	677	A

Version 1.0 of 12.11.2021

Protocol-Specific Version for Protocol #PHS-APIS-004-MEX-SOL-TAV. version 1.3 dated 07.06.2021

CONFIDENTIAL

page 13 of 58

Plan for statistical analysis of efficacy and safety parameters

Country	Block number	Randomization code	Therapy
Republic of Uzbekistan	6	641	B
Republic of Uzbekistan	6	214	A
Republic of Uzbekistan	6	189	A
Republic of Uzbekistan	6	223	B
Republic of Uzbekistan	7	611	A
Republic of Uzbekistan	7	450	B
Republic of Uzbekistan	7	213	B
Republic of Uzbekistan	7	688	A
Republic of Uzbekistan	8	498	B
Republic of Uzbekistan	8	427	A
Republic of Uzbekistan	8	217	B
Republic of Uzbekistan	8	505	A
Republic of Uzbekistan	9	315	B
Republic of Uzbekistan	9	411	A
Republic of Uzbekistan	9	699	B
Republic of Uzbekistan	9	626	A
Republic of Uzbekistan	10	330	A
Republic of Uzbekistan	10	983	B
Republic of Uzbekistan	10	249	B
Republic of Uzbekistan	10	566	A
Russian Federation	11	933	B
Russian Federation	11	393	A
Russian Federation	11	507	B
Russian Federation	11	493	A
Russian Federation	12	524	A
Russian Federation	12	648	B
Russian Federation	12	697	A
Russian Federation	12	912	B
Russian Federation	13	303	A
Russian Federation	13	228	B
Russian Federation	13	802	A
Russian Federation	13	738	B
Russian Federation	14	435	A
Russian Federation	14	732	B
Russian Federation	14	456	A

Version 1.0 of 12.11.2021

Protocol-Specific Version for Protocol #PHS-
APIS-004-MEX-SOL-TAV. version 1.3 dated
07.06.2021

CONFIDENTIAL

page 14 of 58

Plan for statistical analysis of efficacy and safety parameters

Country	Block number	Randomization code	Therapy
Russian Federation	14	279	B
Russian Federation	15	394	B
Russian Federation	15	804	A
Russian Federation	15	274	A
Russian Federation	15	238	B
Russian Federation	16	285	A
Russian Federation	16	160	B
Russian Federation	16	170	B
Russian Federation	16	876	A
Russian Federation	17	846	B
Russian Federation	017	757	A
Russian Federation	017	555	A
Russian Federation	017	131	B
Russian Federation	018	700	A
Russian Federation	018	154	B
Russian Federation	018	132	B
Russian Federation	018	197	A
Russian Federation	019	235	A
Russian Federation	019	835	B
Russian Federation	019	818	B
Russian Federation	019	656	A
Russian Federation	020	291	B
Russian Federation	020	337	A
Russian Federation	020	151	B
Russian Federation	020	785	A
Russian Federation	21	608	B
Russian Federation	21	344	A
Russian Federation	21	770	B
Russian Federation	21	772	A
Russian Federation	022	936	B
Russian Federation	022	923	A
Russian Federation	022	758	A
Russian Federation	022	705	B
Russian Federation	023	902	A
Russian Federation	023	329	B

Version 1.0 of 12.11.2021

Protocol-Specific Version for Protocol #PHS-
APIS-004-MEX-SOL-TAV. version 1.3 dated
07.06.2021

CONFIDENTIAL

page 15 of 58

Plan for statistical analysis of efficacy and safety parameters

Country	Block number	Randomization code	Therapy
Russian Federation	023	198	A
Russian Federation	023	728	B
Russian Federation	024	156	A
Russian Federation	024	402	B
Russian Federation	024	459	B
Russian Federation	024	193	A
Russian Federation	025	999	B
Russian Federation	025	252	A
Russian Federation	025	900	B
Russian Federation	025	306	A
Russian Federation	026	874	B
Russian Federation	026	305	A
Russian Federation	026	173	B
Russian Federation	026	470	A
Russian Federation	027	251	A
Russian Federation	027	155	B
Russian Federation	027	119	B
Russian Federation	027	652	A
Russian Federation	028	613	B
Russian Federation	028	929	A
Russian Federation	028	896	A
Russian Federation	028	492	B
Russian Federation	029	623	A
Russian Federation	029	984	B
Russian Federation	029	761	A
Russian Federation	029	568	B
Russian Federation	030	917	A
Russian Federation	030	599	B
Russian Federation	030	601	B
Russian Federation	030	488	A
Russian Federation	031	447	B
Russian Federation	031	260	A
Russian Federation	031	750	A
Russian Federation	031	877	B
Russian Federation	032	694	B

Version 1.0 of 12.11.2021

Protocol-Specific Version for Protocol #PHS-
APIS-004-MEX-SOL-TAV. version 1.3 dated
07.06.2021

CONFIDENTIAL

page 16 of 58

Plan for statistical analysis of efficacy and safety parameters

Country	Block number	Randomization code	Therapy
Russian Federation	032	169	A
Russian Federation	032	509	A
Russian Federation	032	273	B
Russian Federation	033	428	A
Russian Federation	033	144	B
Russian Federation	033	192	B
Russian Federation	033	469	A
Russian Federation	034	922	B
Russian Federation	034	893	A
Russian Federation	034	253	B
Russian Federation	034	817	A
Russian Federation	035	242	B
Russian Federation	035	811	A
Russian Federation	035	130	B
Russian Federation	035	711	A
Russian Federation	036	609	B
Russian Federation	036	476	A
Russian Federation	036	219	B
Russian Federation	036	395	A
Russian Federation	037	484	B
Russian Federation	037	718	A
Russian Federation	037	290	A
